6.2 Secondary Endpoint Analyses

As this is an open label, Phase I study, secondary endpoints of safety and tolerability will be reported qualitatively. Efficacy will be measured and reported qualitatively by change in Mayo Score, Goebes Histology Index and SIBDQ. As appropriate Student's t test, Mann Whitney U or ANOVA will be used to compare between time points.

1. Active monitoring of UC study patients for TUDCA safety and tolerability

TUDCA has a strong record of safety in several patient populations^{19, 20, 30} (See Detailed Safety Data Review below). However, TUDCA has not been examined specifically in a UC population. Therefore, we aim to define its safety/tolerability in this population through frequent monitoring and symptom assessment as detailed in the study procedures. Adverse events will be categorized according to CTCAE v5.0 criteria and grading.

Infrequent side effects of TUDCA therapy include diarrhea and headache. Our study nurse coordinator will contact all study patients biweekly to assess for any experienced

adverse events. Additionally, in line with WUSM Center for Clinical Trials protocols, patients will have 24 hour access to report suspected Adverse Events. All adverse events or serious adverse events will be recorded and reviewed with treating physician as well as PI. In the event that patients experience an adverse event potentially related to TUDCA, the patient will be offered the option of dose de-escalation or study withdrawal.

TUDCA dose de-escalation strategy: In the setting of a toxicity that the treating physician determines most likely related to TUDCA, we will reduce the dose to 1000 mg (42-50% of initial dose). Common side effects are diarrhea and headache. Since diarrhea is already a symptom implicit to inclusion, we will consider an increase of ≥3 bowel movements/day to be a likely drug toxicity.

Early stopping rules and Dosage Reduction: In the event that ≥50% of patients experience a TUDCA associated side effect or intolerance, we will initiate early study termination or enroll all future patients at the 1000 mg dose. This decision will be made with the guidance of the appointed Data Safety and Monitoring Committee. Full Stopping rules are described in Section 7.4. Note, individual and study stoppage criteria should be applied to these patients as well.

2. Active Monitoring and Management of new elevations in liver transaminases:

The following is our plan to a plan to evaluate subjects for other causes of liver injury and for the potential of drug-induced liver injury (DILI) and include protocol responses to persistent or new deterioration of hepatic function.

For new elevations in transaminases greater than 2x ULN in subjects with normal baseline values or 2x baseline in subjects with abnormal baseline values, repeat measurement should be performed within 48 hours. If elevations persist, subjects should be evaluated for other causes of transaminase elevations and with tests of hepatic function. This may include imaging and/or labs at the treating physicians discretion and, if appropriate, in consultation with the study PI. If no other cause is found then the subjects need to be "Monitored Closely" and the drug should be discontinued as per the recommendations in the Guidance for subjects with normal baseline liver function. For patients with abnormal baseline indices, we will follow the recommendation below.

Recommendation: For patients with normal baseline liver biochemistries, the drug should be discontinued as per: The Guidance for Industry - Drug Induced Liver Injury (Guidance for Industry-Drug Induced Liver Injury: Premarketing Clinical Evaluation at: http://www.fda.gov/downloads/Drugs/.../Guidances/UCM174090.pdf)

The guidance provides recommendations for monitoring and decision-making for drug discontinuation in trials that enroll subjects who have normal liver transaminases and bilirubin at baseline. Drug should be discontinued, and the subject followed until resolution of symptoms or signs in the following situations:

ALT or AST >8x ULN

- ALT or AST >5x ULN for more than 2 weeks
- ALT or AST >3x ULN and (TB >2x ULN or INR >1.5)
- ALT or AST >3x ULN with the appearance of fatigue, nausea, vomiting, right upper quadrant pain or tenderness, fever, rash, and/or eosinophilia (> 5%)

For patients with abnormal baseline indices, see the recommendations below.

- Baseline values should be established (by at least two samples obtained at least 4 weeks and no more than 8-12 weeks apart or up to 16 weeks apart if the potential subject has ≥3 LFT labs in the clinical chart) to account for disease related changes in liver enzymes and bilirubin while on study that may otherwise be inappropriately attributed to study drug. The differences in repeat measurements of baseline serum AST, ALT, ALP and total bilirubin (TBL) should be small (<20%) to be eligible for study entry. You should not enroll subjects with evidence of worsening liver function based on the 2 initial laboratory values used to establish the baseline.

- If subjects with abnormal baseline liver indices develop elevations of AST or ALT >2x baseline or total bilirubin >1.5x baseline values during the study, repeat testing should be performed within 48 -72 hours. If there are persistent elevations (ALT or AST >2x baseline or TBL >1.5x baseline values) upon repeat testing, then close observation (testing and physical examination 2-3 times per week) should be implemented and discontinuation of drug should be considered (see c below).

A decision to discontinue or temporarily interrupt the study drug should be considered based on factors that include how much higher than baseline ALT and AST were relative to the upper limit of normal (ULN) and how much the on study ALT and AST levels have increased relative to baseline, in addition to whether there is concomitant elevation of bilirubin or INR. You need to discontinue or temporarily interrupt the study drug:

- If baseline measurements (BLM) were <2x ULN, discontinue if ALT or AST increases to >5x BLM.
- If BLM ≥2x ULN but <5x ULN, discontinue if ALT or AST increases to >3x BLM
- If BLM ≥ 5x ULN, discontinue if ALT or AST increases to >2x BLM
- Discontinue if ALT or AST increase > 2x BLM AND the increase is accompanied by a concomitant increase in TBL to >2x BLM OR the INR concomitantly increases by >0.2.

In any subjects with signs and symptoms of fatigue, nausea, vomiting, right upper quadrant pain or tenderness, fever, rash, and/or eosinophilia (> 5%).

3. Examine efficacy endpoints endoscopic mucosal healing, clinical response (Mayo Score) as well as histologic severity (Geboes histology index).

We anticipate that TUDCA therapy will reduce ER stress and promote mucosal healing. As TUDCA has the potential to increase stool frequency, it is important to measure efficacy through objective measures (endoscopy and histology) as well as clinical symptoms. Thus, we will obtain a complete Mayo UC score at weeks 0 and 6 and a partial (no endoscopic subscore) at weeks 2 and 4.32 Biopsies will be obtained at both

endoscopic procedures and objectively scored by the Goebes index. Thus, secondary endpoints will include the following using FDA recommended UC Clinical trial guidelines⁴¹:

- 1) Mucosal Healing: A decrease of at least 1 point on the Mayo endoscopic subscore with a final score of 0 or 1 will be used as a marker of mucosal healing.
- 2) Clinical Response: A decrease in Mayo Score of ≥ 3 points and a decrease in Mayo Score of ≥ 30% from baseline and a decrease in the rectal bleeding score of ≥ 1 or an absolute rectal bleeding score of 0-1.
 - a. Clinical Remission will also be recorded if achieved as defined by a total Mayo Score of ≤2 with no subscore >1 and improvement of endoscopic appearance of the mucosa (Mayo 0 or 1).
- **3) Histologic activity:** *Histologic disease activity.* Colon biopsy samples will be harvested and fixed as described. H&E stained sections will be evaluated for tissue damage and inflammation by a gastrointestinal pathologist in a double-blinded manner, using the simplified Geboes histology index^{34, 35}

We expect that TUDCA treatment will significantly alleviate inflammation in colon tissues, which will be correlated with increased plasma concentration of TUDCA or the deconjugated form UDCA. We will collect stool samples both before and after TUDCA treatment for potential (longer range) studies of gut microbiota composition.

Data analysis, interpretation and alternative plans: We expect that there will be minimal adverse effects due to TUDCA treatment, as its safety in humans has been proven in clinical trials for other disease conditions. We expect that TUDCA treatment will improve endoscopic and histologic parameters of inflammation. We also anticipate that it will improve overall Mayo scores and lead to clinical response, if not remission. It is possible though that TUDCA will exacerbate diarrhea in UC patients and clinical symptoms may worsen even if mucosal healing occurs. It is possible that we will not achieve significant improvement in the severity of inflammation, as mucosal healing can take as long as several months (Lialda induction trial) and our TUDCA treatment duration is only 6 weeks. In this case, we will analyze whether expression of ER stress, inflammation and cell death markers in colon biopsy tissues is correlated with the plasma concentration of TUDCA and its metabolites, which will provide a reliable indication for long-term mucosal healing.

7 Safety and Adverse Events

As Safety and tolerability are secondary endpoints, they are further described above in section 6.

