3.1 Inclusion Criteria

- 1) Ages Eligible for Study: 18 Years to 65 Years;
- 2) Confirmed ulcerative colitis disease through radiographic, endoscopic and/or histologic criteria;
- 3) Confirmed with active ulcerative colitis (defined as a complete Mayo score \geq 5 with endoscopic subscore of \geq 1) See Appendix for Mayo Score using recent adaptation to include any friability on endoscopy to be scored as "2".
- 4) On a stable dose of medications for IBD (i.e. no change in medication within 4 weeks of study enrollment) and not planning to initiate new medication other than TUDCA.

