4.3 Method for Assigning Subjects to Treatment Groups

Open label study. All patients will receive TUDCA.

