4.8.6 Return or Destruction of Study Drug

At the completion of the study, there will be a final reconciliation of drug shipped, drug consumed, and drug remaining. This reconciliation will be logged on the drug reconciliation form, signed and dated. Any discrepancies noted will be investigated, resolved, and documented prior to return or destruction of unused study drug. Drug destroyed on site will be documented in the study files.

5 Study Procedures

Table 1 summarize study procedures, complementing Fig 1 above. Also see Appendix 1

	Visit	1	2	3	4	5	5
	Week #	≤ 2 weeks prior to baseline	0	2	4	6	8
vent		Screening	g Baseline	Week2	Week 4	Final visit - 6 weeks	Phone Ca follow up
Visit type	Clinic or Phone call based on clinic visit	х					
	Endoscopy		х			х	
	Phone Call			x	x		x
Coordinator Services	Informed consent	х					
	Inclusion/Exclusion Criteria	х					
	Demographics	х					
	Con Med review	х	х	х	х	х	
	Provide stool collection kit to patient	х					
	Stool Specimen Collection		х			х	
	Phlebotomy (Note LFT's will be drawn between week 2 to 4)		х	х		х	
	Lab Processing		х			х	
	Vital Signs		х			x	
	QoL Questionnaire (SIBDQ)		х	х	х	х	
	Medication Dispensing-CRC		х				
	Medication Accountability			х	х	х	
	Adverse Event Monitoring		х	x	х	x	x
	Telephone Call Assessment/Follow-up			x	x		x
Investigator Services	Partial Mayo Score Assessment			х	х		х
	Full Mayo Score with Endoscopic Score		х			х	
	Medical History for study	х					
Procedure	Sigmoidoscopy/Colonoscopy		х			х	

Endoscopic disease activity. The complete Mayo score will be completed at baseline and after 6 weeks of treatment, based on stool frequency, rectal bleeding, endoscopic findings and physician's global assessment³². In this trial, we are adapting the Mayo Scoring used in the OCTAVE clinical trial program.³³ Whereas standard Mayo scoring designates mild friability as an endoscopic subscore of 1, in the OCTAVE clinical trial program, any sign of friability led to an endoscopic subscore of 2. See Appendix 1.

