6.1 Sample Size Determination for Primary Endpoint

Estimates of change in the primary outcomes: We expect that TUDCA treatment will lead to similar changes on ER stress markers in UC patients as that in IBD mouse models. As judged by quantification results of western blot, the expression levels of ER stress markers in IBD mouse models were significantly reduced by 25% to 45% after TUDCA treatment.⁴ A previous publication, as well as our own data, has shown that standard deviations of the ER stress markers are less than ½ of the means in intestinal biopsy samples of IBD patients⁴⁰. Considering there might be greater variation after the TUDCA treatment, we set the standard deviations at half of the means of all the ER stress markers (Table 2).

Table 2 Sample size calculation

ER stress markers	Difference between means	Estimated standard deviation	Sample size at power=0.8	Sample size at power=0.9
p-elF2α	1.16-0.64=0.52	0.26	5.09	6.39
XBP1s	1.21-0.73=0.48	0.24	5.09	6.39
BIP	1.13-0.84=0.30	0.15	5.09	6.39

Power Estimates for each primary endpoint: We used the quantification results of western blot on ER stress markers to calculate the sample size needed. Since the impact of TUDCA on intestine tissues in humans has not been examined, we used the difference between the mean values of ER stress markers in groups treated with or without TUDCA that we obtained in murine studies.⁴ Power analysis using the R software shows that 7 patients are sufficient to detect the difference before and after the treatment, when P<0.05 is considered significant. Due to the relatively variability in IBD patient disease activity and high dropout rate in IBD clinical trials, we will enroll a total of 12 patients will be recruited for the study with an expected

Statistical analysis: We will be specifically interested in the statistical contrasts that compare before and after TUDCA treatment. Correlation between the primary end point and secondary end point will also be examined. The appropriateness of all analysis of variance and covariance models will be evaluated using regression residuals. If normality or homoscedasticity requirements are violated, data transformations will be explored and, if appropriate transformations cannot be found, analyses may be done semi-parametrically using the ranks of the data.

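### Section 6.2 lists Mann Whitney U, an independent-groups test, for comparing time points measured in the same patients

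*Combined protocol and SAP*

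**What the plan says.** - **Test.** Section 6.2 lists Student's t test first, to be used as appropriate, and continues: "Mann Whitney U or ANOVA will be used to compare between time points". None of the three tests is described as paired or repeated-measures.
- **Outcomes.** The preceding sentence of section 6.2 reads: "Efficacy will be measured and reported qualitatively by change in Mayo Score, Goebes Histology Index and SIBDQ".
- **Design.** Section 4.3: "Open label study. All patients will receive TUDCA". There is no comparison group.
- **Timing.** Section 5: "The complete Mayo score will be completed at baseline and after 6 weeks of treatment". Section 6.2, item 3, repeats that "we will obtain a complete Mayo UC score at weeks 0 and 6" and adds partial Mayo scores at weeks 2 and 4. Table 1 schedules the SIBDQ at baseline and at weeks 2, 4 and 6. Biopsies for Geboes scoring are taken at both endoscopies.
- **Other mention of ranks.** For the primary markers, section 6.1 says that if model assumptions fail and no transformation helps, "analyses may be done semi-parametrically using the ranks of the data". It names no test.

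**The concern.** With one arm, the two samples in any time-point comparison are the same patients seen twice. Student's t and ANOVA have paired or repeated-measures versions, so for them the missing word is only a clarification. Mann Whitney U has no such version, so no before/after comparison in this trial is one for which it is appropriate.

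The listing matters because Mayo and Geboes are ordinal and there are at most 12 patients, a setting in which an analyst may well want a rank test. The plan names just this one. At stake is the power of the secondary comparisons: a real before/after change in symptoms, histology or quality of life could be reported as not significant because the test ignored the pairing.

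**Working it through.** Section 6.2 gives no numerical figure for these comparisons, so there is none to reproduce. The check asks what is lost if Mann Whitney U is applied to paired data.

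**Inputs**
- From the documents: 12 patients (section 6.1), one arm (section 4.3), the same patients at weeks 0 and 6 (sections 5 and 6.2), and P<0.05 as the significance level (stated in section 6.1 for the primary markers; taken here as two-sided).
- Assumed, because the documents do not give them: before/after correlation ρ of 0, 0.3, 0.5 or 0.7; a shift of 0.8 SD; normal data with equal SDs at the two times.

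**Step 1: why pairing matters.** With common SD σ and n pairs, the variance of the mean change is 2σ²(1 − ρ)/n. An independent-groups test works as if it were 2σ²/n. When ρ is positive, that overstates the noise. A paired test sees a standardised change of shift / √(2(1 − ρ)). For a shift of 0.8 SD:
- ρ = 0: 0.8 / √2.0 = 0.57
- ρ = 0.3: 0.8 / √1.4 = 0.68
- ρ = 0.5: 0.8 / √1.0 = 0.80
- ρ = 0.7: 0.8 / √0.6 = 1.03

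The paired signal grows with ρ. The independent-groups test does not benefit.

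**Step 2: simulation.** 100,000 simulated trials per setting, 12 pairs, exact null distributions, two-sided 5%.

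| Assumed ρ | Type I error, Mann Whitney | Type I error, signed-rank | Power at 0.8 SD, Mann Whitney | Power at 0.8 SD, signed-rank |
|---|---|---|---|---|
| 0 | 4.5% | about 4.3% | 43% | 39% |
| 0.3 | 2.0% | about 4.3% | 42% | 52% |
| 0.5 | 0.9% | about 4.3% | 41% | 67% |
| 0.7 | 0.2% | about 4.3% | 41% | 87% |

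A separate simulation of 40,000 trials per setting agreed to within about 1 percentage point. The power difference in favour of signed-rank is 39 − 43 = −4 points at ρ = 0, then 52 − 42 = 10, 67 − 41 = 26 and 87 − 41 = 46 points.

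**Step 3: missing week 6 values.** Signed-rank uses complete pairs only. If 2 of 12 patients lack week 6 (assumed), signed-rank on 10 pairs has 35 / 46 / 60 / 81% power at the same shift and correlations. Mann Whitney on 12 baselines and 10 week 6 values has 38 / 37 / 36 / 36%. The ordering is unchanged.

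**Step 4: what is not affected.** Mucosal healing, clinical response and remission in section 6.2, item 3, are read from each patient's own scores and use none of these tests. The primary marker analysis is described in section 6.1, which does not name Mann Whitney U.

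**The case against.** **The plan does not require Mann Whitney U.** It offers three tests, to be used as appropriate. If the t test is chosen and run paired, nothing is lost: at ρ of 0.5 and 0.7 its power is around 71% and 90% at a 0.8 SD shift. This stands. The harm arises only if Mann Whitney U is chosen. The latitude permits avoiding the test, but it does not make the test fit paired data.

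**The outcomes are secondary and reported qualitatively.** This also stands and limits the weight. It does not remove the point, because the next sentence of section 6.2 commits to hypothesis tests.

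**A reader might infer that the primary analysis is unpaired too.** Table 2's 5.09 and 6.39 do reproduce as patients per group from a two-sample t test with difference/SD of 2. But that is the sample-size calculation. The analysis text in section 6.1 speaks of contrasts before and after treatment, and its rank fallback names no independent-groups test. The documents do not support extending this point to section 6.1.

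**A reader might infer that Mann Whitney U merely hides a drug effect, or always keeps false positives below 5%.** Neither follows. Section 3.1 selects patients with a complete Mayo score of at least 5, so scores can fall without any drug effect. Assume integer scores, a population mean of 6, SD 2 and no drug effect. Enrolled patients then improve by about 0.8 points at ρ = 0 and 0.6 at ρ = 0.3. Mann Whitney rejects in about 15% and 7% of trials, and signed-rank in about 14% and 11%. At an assumed mean of 8 the effect is negligible. The type I errors in the table above therefore refer to no before/after change, not to no drug effect.

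**Conclusion.** The point holds as a defect in one sentence of section 6.2: an independent-groups test is listed for comparisons that are all within patient, and it is the only rank test named. If it is used, the cost is power to detect a before/after change. The difference is about 10, 26 and 46 percentage points at assumed correlations of 0.3, 0.5 and 0.7, for an assumed 0.8 SD shift in 12 pairs with normal data. At correlation 0 there is no loss; Mann Whitney is then about 4 points ahead.

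The reach is limited to supportive secondary comparisons of Mayo, Geboes and SIBDQ. The correction is worth making because it is specific and nearly free, not because the trial's main conclusions depend on it. A paired test answers whether scores changed. Without a control group it cannot say that the drug changed them.

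**What to change.** In section 6.2 only, replace the sentence on tests with:

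> Week 0 and week 6 values will be compared within patient by paired t-test or Wilcoxon signed-rank test; outcomes measured at more than two visits will be compared by repeated-measures ANOVA or, for ordinal scores, the Friedman test. For Geboes, one value per patient per visit, from the inflamed site, will be used. The number of patients with both measurements will be reported.

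The Friedman option is there for partial Mayo, which is ordinal and scored at several visits. The Geboes sentence is needed because section 5 has all biopsy specimens scored, from inflamed and, where available, non-inflamed tissue, while a paired test needs one value per visit. No change to section 6.1 follows from this point.

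Cost: a few sentences and no new data, visits or patients. Signed-rank gives up a few power points if the correlation is near zero (about 4 at a 0.8 SD shift), and only patients with both measurements contribute.

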4.2 Treatment Regimen

A weight based regimen for TUDCA will be used, administering it in 3 divided doses which corresponds to an average dose of 20-25 mg/kg/day accordingly using 1750 mg daily for patients <75 kg and 2000 mg daily for patients ≥75 kg.

It has been shown that TUDCA at the dose of 25mg/Kg/day can achieve maximum composition in the serum and bile in patients with primary biliary cirrhosis¹⁹. Previous clinical studies also have shown that 1 to 6 months of TUDCA treatment with 1750mg/day is efficacious and safe in patients with different diseases, including primary biliary cirrhosis^{19, 27, 28}, liver cirrhosis²⁹, HCV-related chronic hepatitis³⁰ and insulin resistance¹⁷. Animal studies also suggest that TUDCA appears to be very well tolerated even at high doses.

Patients will not be charged for the drug. This will be supplied in original packaging by Bruschettini Srl, Genoa, Italy. TUDCA distribution will be carried out by our Investigational Pharmacy at Washington University. Patients will receive a 6 week supply at initiation visit.

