4.8.4 Study Drug discontinuation

All subjects who discontinue study drug should be considered withdrawn from the study and should complete the study completion visit assessments. If subjects fail to return for these visits, or are unable to do so, every effort will be made by the investigator to contact them or a knowledgeable informant by telephone or by

sending appropriate correspondence (i.e. certified letter) that will become part of the investigator's file to record that efforts were made to reach the subjects.

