7.4 Stopping Rules

Individual stoppage criteria-

Based on extensive clinical trial data, we anticipate that TUDCA will be well tolerated. However, patients will be monitored via study visits and phone calls and will permanently discontinue study drug for any adverse event possibly or probably related to study drug that is considered of *moderate or severe intensity*. To define intensity, we will utilize a standard severity rating scale to ensure this safety monitoring plan is enforced in a standardized fashion. Individual subjects should be discontinued for any adverse event rated a Grade 3 or greater in severity on the Common Terminology Criteria for Adverse Events (CTCAE_v5.0 November 2017) scale v, unless it is clearly related to the underlying disease.

For disease specific symptoms (e.g. diarrhea, rectal bleeding) we will consider disease worsening as an increase in >3 points on the Mayo Score to be potentially related to TUDCA and will lower the dose to 1000 mg as described. If symptoms persist or worsen over the subsequent 5 days, the patient will be permanently discontinued from the study.

Study stoppage criteria-

Enrollment of new subjects should be interrupted should 2 or more patients experience CTCAE Grade 3 event, or 1 or more patients experience CTCAE Grade 4 events not clearly related to the underlying disease. Study enrollment may be resumed following review of all available safety data by the investigator and study team and a concurrent opinion that the totality of the data suggests this event is unlikely to be related to TUDCA. The study should be terminated if, following the review of the safety data, it has not been possible to demonstrate that the adverse event has a clear relationship to the underlying disease or associated co-morbidity.

We will initiate early study termination or enroll all future patients at the 1000 mg dose. This decision will be made with the guidance of the appointed Data Safety and Monitoring Committee. Individual and study stoppage criteria should be applied to these patients as well.

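### If any patient's dose is reduced or stopped for worsening symptoms, the planned correlation of tissue findings with plasma TUDCA partly reflects the dose rules and should not be read as exposure-response

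*Combined protocol and SAP*

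**What the plan says.** Section 6.2 raises the plasma correlation twice.

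- Under histologic activity it is an expectation: inflammation will fall, "which will be correlated with increased plasma concentration of TUDCA or the deconjugated form UDCA".
- Under data analysis and alternative plans it is an analysis, to be done if the severity of inflammation does not improve significantly. The question is whether ER stress, inflammation and cell death markers in the biopsies show an expression that "is correlated with the plasma concentration of TUDCA and its metabolites, which will provide a reliable indication for long-term mucosal healing".

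The starting dose (Section 4.2) is set by weight, "using 1750 mg daily for patients <75 kg and 2000 mg daily for patients ≥75 kg". Two rules then tie the later dose to the clinical course.

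- Section 6.2, de-escalation: for a toxicity judged most likely drug-related, "we will reduce the dose to 1000 mg". Three or more additional bowel movements a day count as likely toxicity.
- Section 7.4: the protocol will consider "an increase in >3 points on the Mayo Score to be potentially related to TUDCA and will lower the dose to 1000 mg". If symptoms persist or worsen over the next five days, the patient is permanently discontinued.

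Section 5 measures bile acids at the start of treatment, at week 2 and at endoscopy, so the last sample coincides with the outcome biopsy. On stopping, Section 4.8.4 says "All subjects who discontinue study drug should be considered withdrawn from the study and should complete the study completion visit assessments", whereas Section 4.8.5 leaves those assessments after withdrawal to the investigator. No section states which sample enters the correlation or how reduced or stopped patients are treated in it.

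**The concern.** An exposure-response reading needs exposure to be free of the outcome. Here worsening symptoms lower the dose, the lower dose lowers later plasma TUDCA, and that plasma value is paired with a biopsy from the same patient at the same visit. If symptoms track tissue at all, poor tissue outcomes are matched with low concentrations even when the drug does nothing. The resulting sign is the one the sponsor hopes for.

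This matters most for the fallback. It is reached when inflammation has not improved, and Section 6.2 already says the correlation will be a dependable pointer to healing. A trial with no effect could then report a favourable exposure-response finding produced in part by its own dose rules. Perfectly timed samples or a larger trial would not remove this bias.

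**Working it through.** **Plan's own figure.** None is given for this analysis. The only sample-size figures (Section 6.1, Table 2) concern the before-after change in ER stress markers.

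**Inputs from the documents.** 12 patients, single arm. Starting dose 1750 or 2000 mg, reduced dose 1000 mg. Significance at P<0.05, taken here as two-sided.

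**Size of the dose change.** 1000/1750 = 57.1% and 1000/2000 = 50.0%, so the cut is 42.9% to 50.0%. Section 6.2 gives the reduced dose as 42-50% of the initial dose. That does not match its own figures and must be reconciled, but it does not affect this point.

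**Critical value.** With n = 12, t(0.975, 10 df) = 2.228, so the critical |r| = 2.228/√(2.228² + 10) = 0.576.

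**Assumptions, none given in the documents.** The number of patients reduced or stopped; symptom-tissue correlation ρ (0.6, range 0.2 to 0.8); plasma = current dose × lognormal variation with CV 50%; no effect of exposure on tissue.

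**Method.** Draw tissue improvement Y ~ N(0,1) and symptom change S = ρY + √(1−ρ²)·e, with e ~ N(0,1). Give the k patients with the worst S 1000 mg. Compute Spearman's correlation of week-6 plasma with Y, and count results with p<0.05 and r>0. The nominal rate is 2.5%.

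| Patients reduced (of 12) | ρ | False findings in the hoped-for direction |
|---|---|---|
| 0 | any | 2.5% |
| 1 | 0.6 | about 4% |
| 2 | 0.6 | about 7% |
| 3 | 0.6 | about 9% (mean r about 0.20) |
| 3 | 0.2 to 0.8 | 4% to 13% |
| 3 | 0 | nominal |

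**If stopped patients also supply a final sample** (ρ = 0.6, brackets 0.4 to 0.8): two reduced and one off drug gives about 12% (7-18%); two reduced and two off drug gives about 18% (10-30%).

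**A second calculation**, with Pearson's correlation, CV 30-50% and ρ 0.3 to 0.7, gives 4-15% with three reduced and 7-28% with three stopped.

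**Relaxing proportionality** (three reduced, ρ = 0.6). If plasma varies with the square root of dose, the rate falls to about 6%. On a full plateau it returns to about nominal.

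**Checking two possible repairs** (same setting).

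- *Concentration divided by current dose.* This is correct only if exposure is proportional to dose. Under square-root dependence the mean r is −0.11, with about 5.5% false findings in the opposite direction. On a plateau the mean r is −0.20, with 8.9%.
- *Last on-drug sample before any dose change.* The rate stays at about 2.5% in every setting tried.

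**The case against.** The strongest reply is that the size is assumed. The documents give no reduction rate. The triggers are absolute (a Mayo rise above 3 points, three or more extra bowel movements a day, or another toxicity judged drug-related), Section 6.2 expects few adverse effects, and Section 1.2 cites ten adults treated at 1.75 g/day with none. This stands: with nobody reduced or stopped the path adds no bias, and with one patient it is small. A reader might infer that the protocol guarantees a spurious correlation. It does not; it creates the route and leaves it open.

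Second, the triggers are symptoms, not histology. Section 6.2 accepts that symptoms may worsen while the mucosa heals, and the documents do not quantify how the fallback's markers relate to symptoms. This also stands, and is why the range goes down to ρ = 0.2 and the zero case is shown.

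Third, a reader might take the 12% and 18% figures as the expected size. They require stopped patients to attend the final visit and be analysed. Sections 4.8.4 and 4.8.5 differ on attendance and must be reconciled, and nothing says withdrawn patients enter the correlation.

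Fourth, Sections 1.5 and 4.2 say that 25 mg/kg/day achieves the maximum composition in serum and bile, so a plateau is possible. That would shrink or remove the artefact.

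Finally, the histology sentence is only an expectation, and the fallback is a contingent analysis in a 12-patient Phase I study. This lowers the severity. It does not justify the claim in Section 6.2 that the correlation reliably indicates healing.

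**Conclusion.** The point holds in conditional form. If any patient is reduced or stopped for worsening, a low week-6 concentration is partly a consequence of a poor course, and the plan has no rule that separates the two. Under no drug effect, proportional plasma, CV 50% and ρ = 0.6, the false-finding rate in the hoped-for direction goes from 2.5% to about 4%, 7% and 9% with one, two and three of 12 reduced; across ρ 0.2 to 0.8 with three reduced it is 4-13%. It is higher if stopped patients contribute final samples, and nil if nobody is reduced or stopped, if symptoms and tissue are unrelated, or if plasma is at a plateau.

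The documents do not support saying that a positive correlation would be wholly an artefact: the mean r of about 0.20 with three reduced is well below the 0.576 needed for significance. What they do support is that unadjusted week-6 concentrations cannot be presented as exposure-response evidence. Severity is minor: neither the primary endpoint nor any safety decision depends on this analysis.

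**What to change.** In Section 6.2, before data are seen:

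1. Define the exposure measure as the last on-drug plasma sample taken before any dose reduction or stop: week 2 for patients later reduced or stopped, week 6 for those unchanged. Week 2 for everyone is also acceptable and avoids mixing sampling times.
2. Compare the actual draw date with the date of any dose change. Section 5 collects this blood with the safety labs, and Table 1 allows the liver tests to be drawn between weeks 2 and 4.
3. Plot reduced and stopped patients as marked points, and report the coefficient with and without them.
4. Replace the claim that the correlation reliably indicates long-term healing with a statement that it is exploratory and that unadjusted week-6 concentrations are not evidence of exposure-response.
5. Do not divide concentration by current dose; unless exposure is proportional to dose, this biases the correlation the other way.

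The cost is analysis wording only. The samples are already planned, and no dose or clinical rule changes. The downside is that a patient reduced or stopped before the week 2 sample has no usable exposure value and leaves the coefficient.
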